5.3.3.4 Abnormal Laboratory Values

Not every laboratory abnormality qualifies as an AE. A laboratory test result must be reported as an AE if it meets any of the following criteria:

- Is accompanied by clinical symptoms
- Results in a change in study treatment (e.g., dosage modification, treatment interruption, or treatment discontinuation)

Alteplase—Genentech, Inc.
51/Protocol ML29093, Version 3

- Results in a medical intervention (e.g., potassium supplementation for hypokalemia) or a change in concomitant therapy
- Is clinically significant in the investigator's judgment

It is the investigator's responsibility to review all laboratory findings. Medical and scientific judgment should be exercised in deciding whether an isolated laboratory abnormality should be classified as an AE.

If a clinically significant laboratory abnormality is a sign of a disease or syndrome (e.g., alkaline phosphatase and bilirubin 5 times the upper limit of normal associated with cholestasis), only the diagnosis (i.e., cholestasis) should be recorded on the Adverse Event eCRF.

If a clinically significant laboratory abnormality is not a sign of a disease or syndrome, the abnormality itself should be recorded on the Adverse Event eCRF, along with a descriptor indicating if the test result is above or below the normal range (e.g., "elevated potassium" as opposed to "abnormal potassium"). If the laboratory abnormality can be characterized by a precise clinical term per standard definitions, the clinical term should be recorded as the AE. For example, an elevated serum potassium level of 7 mEq/L should be recorded as "hyperkalemia."

Observations of the same clinically significant laboratory abnormality from visit to visit should *only* be recorded *once* on the Adverse Event eCRF (*see Section 5.3.3.3 for details on recording persistent AEs*).

5.3.3.5 Abnormal Vital Sign Values

Not every vital sign abnormality qualifies as an AE. A vital sign result must be reported as an AE if it meets any of the following criteria:

- Is accompanied by clinical symptoms
- Results in a change in study treatment (e.g., dosage modification, treatment interruption, or treatment discontinuation)
- Results in a medical intervention or a change in concomitant therapy
- Is clinically significant in the investigator's judgment

It is the investigator's responsibility to review all vital sign findings. Medical and scientific judgment should be exercised in deciding whether an isolated vital sign abnormality should be classified as an AE.

If a clinically significant vital sign abnormality is a sign of a disease or syndrome (e.g., high blood pressure), only the diagnosis (i.e., hypertension) should be recorded on the Adverse Event eCRF.

Observations of the same clinically significant vital sign abnormality from visit to visit should *only* be recorded *once* on the Adverse Event eCRF (see Section 5.3.3.3 for details on recording persistent AEs).

5.3.3.6 Deaths

All deaths that occur during the protocol-specified AE reporting period (Section 5.3.1) regardless of relationship to study drug, must be recorded on the Adverse Event eCRF and immediately reported to the Sponsor (see Section 5.2.2). This includes death attributed to progression of AIS.

Death should be considered an outcome and not a distinct event. The event or condition that caused or contributed to the fatal outcome should be recorded as the single medical concept on the Adverse Event eCRF. Generally, only one such event should be reported. The term "sudden death" should only be used for the occurrence of an abrupt and unexpected death due to presumed cardiac causes in a patient with or without preexisting heart disease, within 1 hour of the onset of acute symptoms or, in the case of an unwitnessed death, within 24 hours after the patient was last seen alive and stable. If the cause of death is unknown and cannot be ascertained at the time of reporting, "unexplained death" should be recorded on the Adverse Event eCRF. If the cause of death later becomes available (e.g., after autopsy), "unexplained death" should be replaced by the established cause of death.

If the death is attributed to progression of AIS, "acute ischemic stroke progression" should be recorded on the Adverse Event eCRF.

5.3.3.7 Preexisting Medical Conditions

A preexisting medical condition is one that is present at the screening visit for this study. Such conditions should be recorded on the General Medical History and Baseline Conditions eCRF.

A preexisting medical condition should be recorded as an AE only if the frequency, severity, or character of the condition worsens during the study. When recording such events on the Adverse Event eCRF, it is important to convey the concept that the preexisting condition has changed by including applicable descriptors (e.g., more frequent headaches").

5.3.3.8 Lack of Efficacy or Worsening of Acute Ischemic Stroke

Medical occurrences or symptoms of deterioration that are considered part of the disease course or disease process should be recorded as an AE if judged by the investigator to have unexpectedly worsened in severity or frequency or unexpectedly changed in nature at any time during the study. If there is uncertainty, it should be reported as an AE. When recording unexpected worsening of AIS on the Adverse Event eCRF, it is important to convey the concept that the condition has changed by including applicable descriptors of the event.

Alteplase—Genentech, Inc.
53/Protocol ML29093, Version 3

5.3.3.9 Hospitalization or Prolonged Hospitalization

Any AE that results in hospitalization (i.e., in-patient admission to a hospital) or prolonged hospitalization should be documented and reported as an SAE (per the definition of an SAE in Section 5.2.2), except as outlined below.

The following hospitalization scenarios are not considered to be AEs:

- Hospitalization for respite care
- Hospitalization for a preexisting condition, provided that all of the following criteria are met:
 - The hospitalization was planned prior to the study or was scheduled during the study when elective surgery became necessary because of the expected normal progression of the disease.
 - The patient has not suffered an AE.

5.3.3.10 Adverse Events Associated with an Overdose or Error in Drug Administration

An overdose is the accidental or intentional use of a drug in an amount higher than the dose being studied. An overdose or incorrect administration of study treatment is not itself an AE, but it may result in an AE. All AEs associated with an overdose or incorrect administration of study drug should be recorded on the Adverse Event eCRF. If the associated AE fulfills *seriousness* criteria, the event should be reported to the Sponsor immediately (i.e., no more than 24 hours after learning of the event; see Section 5.4.1).

5.3.3.11 Patient-Reported Outcome Data

AE reports will not be derived from PRO data by the Sponsor, and safety analyses will not be performed using PRO data. However, if any PRO responses suggestive of a possible AE are identified during site review of the PRO data, the investigator will determine whether the criteria for an AE have been met and, if so, will report the event on the Adverse Event eCRF.

5.4 IMMEDIATE REPORTING REQUIREMENTS FROM INVESTIGATOR TO SPONSOR

Certain events require immediate reporting to allow the Sponsor to take appropriate measures to address potential new risks in a clinical trial. The investigator must report such events to the Sponsor immediately; under no circumstances should reporting take place more than 24 hours after the investigator learns of the event. The following is a list of events that the investigator must report to the Sponsor within 24 hours after learning of the event, regardless of relationship to study drug:

- SAEs (see Section 5.4.2 for further details)
- Non-serious AESIs (see Section 5.4.2 for further details)
- Pregnancies (see Section 5.4.3 for further details)

The investigator must report new significant follow-up information for these events to the Sponsor immediately (i.e., no more than 24 hours after becoming aware of the information). New significant information includes the following:

- New signs or symptoms or a change in the diagnosis
- Significant new diagnostic test results
- Change in causality based on new information
- Change in the event's outcome, including recovery
- Additional narrative information on the clinical course of the event

Investigators must also comply with local requirements for reporting SAEs to the local health authority and Institutional Review Board/Ethics Committee (IRB/EC).

5.4.1 Emergency Medical Contacts

Medical Monitor Contact Information

PPD Medical Monitor contact information:

Medical Monitor: [REDACTED], M.D.

Telephone Nos.: [REDACTED]

Alternate Medical Monitor contact information for all sites:

Medical Monitor: [REDACTED], M.D.

Telephone No.: [REDACTED]

5.4.2 Reporting Requirements for Serious Adverse Events and Non-Serious Adverse Events of Special Interest

After initiation of study drug, SAEs and non-serious AESIs will be reported until 90 days after the last dose of study drug. Investigators should record all case details that can be gathered immediately (i.e., within 24 hours after learning of the event) on the Adverse Event eCRF and submit the report via the electronic data capture (EDC) system. A report will be generated and sent to Safety Risk Management by the EDC system.

In the event that the EDC system is unavailable, the Serious Adverse Event/Adverse Event of Special Interest Reporting Form provided to investigators should be completed and submitted to the Sponsor or its designee immediately (i.e., no more than 24 hours after learning of the event), either by faxing or by scanning and emailing the form using the fax number or email address provided to investigators (and below). Once the EDC system is available, all information will need to be entered and submitted via the EDC system.

Sites:

[contact]

Alternate [contact]

Alteplase—Genentech, Inc.
55/Protocol ML29093, Version 3

Instructions for reporting post-study AEs are provided in Section 5.6.

5.4.3 Reporting Requirements for Pregnancies

5.4.3.1 Pregnancies in Female Patients

Female patients of childbearing potential will be instructed to immediately inform the investigator if they become pregnant within 30 (± 7) days after the last dose of study drug. A Pregnancy Report eCRF should be completed by the investigator immediately (i.e., no more than 24 hours after learning of the pregnancy) and submitted via the EDC system. A pregnancy report will automatically be generated and sent to Safety Risk Management. Pregnancy should not be recorded on the Adverse Event eCRF. The investigator should counsel the patient, discussing the risks of the pregnancy and the possible effects on the fetus. Monitoring of the patient should continue until conclusion of the pregnancy. Any SAEs associated with the pregnancy (e.g., an event in the fetus, an event in the mother during or after the pregnancy, or a congenital anomaly/birth defect in the child) should be reported on the Adverse Event eCRF.

In the event that the EDC system is unavailable, *the Clinical Trial Pregnancy Reporting Form provided to investigators* should be completed and *submitted to the Sponsor or its designee immediately* (i.e., no more than 24 hours after learning of the pregnancy), *either by faxing or scanning and emailing the form using the fax number or email address provided to investigators*. Once the EDC system is available, all information will need to be entered and submitted via the EDC system.

5.4.3.2 Congenital Anomalies/Birth Defects and Abortions

Any congenital anomaly/birth defect in a child born to a female patient exposed to study drug should be classified as an SAE, recorded on the Adverse Event eCRF, and reported to the Sponsor immediately (i.e., no more than 24 hours after learning of the event; see Section 5.4.1). Any spontaneous abortion should be reported in the same fashion (as the Sponsor considers spontaneous abortions to be medically significant events).

5.5 FOLLOW-UP OF PATIENTS AFTER ADVERSE EVENTS

5.5.1 Investigator Follow-Up

The investigator should follow each AE until the event has resolved to baseline grade or better and is assessed as stable by the investigator, the patient is lost to follow-up, or the patient withdraws consent. Every effort should be made to follow all SAEs considered to be related to study drug or trial-related procedures until a final outcome can be reported.

During the study period, resolution of AEs (with dates) should be documented on the Adverse Event eCRF and in the patient's medical record to facilitate source data verification.

Alteplase—Genentech, Inc.
56/Protocol ML29093, Version 3

All pregnancies reported during the study should be followed until pregnancy outcome. If the EDC system is not available at the time of pregnancy outcome, follow reporting instructions provided in Section 5.4.3.

5.5.2 Sponsor Follow-Up

For SAEs, AESIs, and pregnancies, the Sponsor or a designee may follow up by telephone, fax, electronic mail, and/or a monitoring visit to obtain additional case details and outcome information (e.g., from hospital discharge summaries, consultant reports, autopsy reports) in order to perform an independent medical assessment of the reported case.

5.6 POST-STUDY ADVERSE EVENTS

At the time of study completion or study discontinuation, the investigator should instruct each patient to report to the investigator any subsequent AEs that the patient's personal physician believes could be related to prior study drug treatment or study procedures.

The investigator is not required to actively monitor patients for AEs after the end of the AE reporting period (defined as 90 days after administration of study drug *for SAEs and non-serious AESIs, and 30 days for non-serious AEs*). However, the Sponsor should be notified if the investigator becomes aware of any SAE, death, development of cancer, or a congenital anomaly/birth defect in a subsequently conceived offspring of a female patient exposed to study drug *within 90 days after administration of study drug*.

The investigator should report these events directly to *the Sponsor* via telephone at [name].

5.7 EXPEDITED REPORTING TO HEALTH AUTHORITIES, INVESTIGATORS, INSTITUTIONAL REVIEW BOARDS, AND ETHICS COMMITTEES

The Sponsor will promptly evaluate all SAEs and non-serious AESI against cumulative product experience to identify and expeditiously communicate possible new safety findings to investigators, IRBs, ECs, and applicable health authorities based on applicable legislation.

To determine reporting requirements for single AE cases, the Sponsor will assess the expectedness of these events using the following reference document:

- Alteplase USPI

The Sponsor will compare the severity of each event and the cumulative event frequency reported for the study with the severity and frequency reported in the applicable reference document.

Reporting requirements will also be based on the investigator's assessment of causality and seriousness, with allowance for upgrading by the Sponsor as needed.

Alteplase—Genentech, Inc.
57/Protocol ML29093, Version 3

6. STATISTICAL METHODS

This study will test whether treatment of patients with mild stroke with IV alteplase will lead to a higher proportion (9% absolute difference) of patients with a favorable outcome (mRS of 0 or 1) at 90 days.

6.1 DETERMINATION OF SAMPLE SIZE

A sample size of 856 is required in order to achieve 80% power in the primary analysis to detect an effect size of 9% absolute difference in the proportion of patients with favorable outcomes between the alteplase and control arms. The above sample size calculation assumes a control proportion of 65% and Type I error probability of 0.025 (one-sided), and uses a group sequential design with one interim analysis for futility (non-binding), based on an O'Brien-Fleming boundary, after 50% of the anticipated sample size have completed the 90-day follow-up assessments. [REDACTED] was used for this sample size calculation.

The ITT principle will be applied to the primary analysis and, therefore, to safeguard against dilution of the treatment effect associated with an approximate 5% non-adherence rate (due to lost to follow-up, consent withdrawal, treatment crossovers, and stroke mimics), the above sample size needs to be inflated by a factor of 1/0.95² or 1.108 ([Friedman et al. 1998](#)). Therefore, a total sample size of 948 is required for this study.

6.2 PRIMARY ANALYSIS

The primary efficacy analysis will test the hypothesis of superiority of IV alteplase therapy over standard medical care in AIS patients with mild deficits. The primary efficacy outcome is the proportion of patients with a favorable outcome, defined by mRS score of 0 or 1 at 90 days post-randomization. The difference in the proportion of mRS 0–1 responders (favorable outcome) at 90 days post-randomization between the IV alteplase arm and the standard medical care arm will be compared via a Cochran-Mantel-Haenszel test, stratified by pre-treatment NIHSS score (0–2 vs. 3–5), age (<65 vs. ≥65), and last known well time to treatment (0–2 hours vs. >2–3 hours). The primary efficacy analysis will include all randomized patients, with patients grouped according to the treatment assigned at randomization adhering to the ITT principle. As a sensitivity analysis, results from the univariate Pearson's chi-square test will also be presented.

As a supportive, secondary analysis, an ordinal (or "shift") analysis of the distribution of the mRS will be analyzed via proportional odds model if the proportionality assumption holds, and by the Mann-Whitney superiority measure if the proportionality assumption does not hold. The proportionality assumption will be assessed using the score test as well as clinical judgment on the similarities of the different odds ratios. As a secondary efficacy outcome, the global outcome score at 90 days will be analyzed using the global odds ratio test based on the generalized estimating equations analysis (Wald-type χ^2)

Alteplase—Genentech, Inc.
58/Protocol ML29093, Version 3

test) with unstructured covariance-correlation matrix. These results will be treated as supportive evidence (or lack thereof) of the treatment effect rather than conclusive evidence. The significance of each test is determined at the two-sided alpha level of 0.05. The specific statistical model for analyzing each of these outcome measures will be detailed in the Statistical Analysis Plan (SAP).

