4.1.2 Exclusion Criteria

Patients who meet any of the following criteria will be excluded from study entry:

- CT or MRI findings consisting of one of the following:
 - CT with clear large hypodensity that is greater than one-third middle cerebral artery (MCA) territory (or greater than 100 cc if not in MCA territory),
 - MRI with clear large hyperintensity on concurrent diffusion-weighted (DW) and fluid-attenuated inversion recovery (FLAIR) that is greater than one-third MCA territory (or greater than 100 cc if not in MCA territory),
 - Imaging lesion consistent with acute hemorrhage of any degree, OR
 - Evidence of intraparenchymal tumor
- Disability prior to the presenting stroke (historical mRS score ≥ 2)
- Standard contraindications to IV alteplase for patients treated within 3 hours of symptom onset, including:
 - Head trauma or previous stroke within the previous 3 months
 - Myocardial infarction within the previous 3 months
 - Gastrointestinal or urinary tract hemorrhage within the previous 21 days
 - Major surgery within the previous 14 days
 - Arterial puncture at a non-compressible site within the previous 7 days
 - Any history of ICH with the exception of <5 chronic microbleeds on MRI
 - Elevated blood pressure (systolic >185 mm Hg or diastolic >110 mm Hg), or the use of aggressive measures (use of more than two intravenous agents to lower blood pressure) to achieve blood pressure within acceptable parameters
 - Treatment with unfractionated heparin within the last 48 hours and activated partial thromboplastin time (aPTT) outside of the normal range as specified by the center's local laboratory
 - Blood glucose <50 mg/dL
 - International normalized ratio (INR) >1.7 (Note: This does not need to be verified prior to randomization if there is no clinical suspicion of abnormality.)
 - Platelet count of $<100,000/\text{mm}^3$ (Note: This does not need to be verified prior to randomization if there is no clinical suspicion of abnormality.)
 - Treatment with a direct thrombin inhibitor or factor Xa inhibitor (including novel oral anticoagulants [e.g., dabigatran, rivaroxaban, apixaban, edoxaban]) within the last 48 hours
 - Treatment with a low-molecular-weight heparin (e.g., dalteparin, enoxaparin) within the last 48 hours
- Allergic reactions to study drug, aspirin, *or* nonsteroidal anti-inflammatory drugs (NSAIDs)

Alteplase—Genentech, Inc.
33/Protocol ML29093, Version 3

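### The primary CMH test uses NIHSS, age and time to treatment only as two-level factors, at a small cost in efficiency that full-scale adjustment would recover

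*Protocol*

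**What the plan says.** Section 6.2 compares the proportions with mRS 0–1 at Day 90 by a CMH test "stratified by pre-treatment NIHSS score (0–2 vs. 3–5), age (<65 vs. ≥65), and last known well time to treatment", the last factor cut at 2 hours. Three two-level factors make eight strata. The only other test of the primary endpoint named there is unadjusted: "As a sensitivity analysis, results from the univariate Pearson's chi-square test will also be presented".

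Section 6.1 gives the design: "A sample size of 856 is required in order to achieve 80% power in the primary analysis", the target being a gain of 9 percentage points. It "assumes a control proportion of 65% and Type I error probability of 0.025 (one-sided", with one non-binding futility look at half the information. No credit is taken for baseline covariates.

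On the covariates themselves:
- Section 4.6.1 and Appendix 1 collect a full NIHSS score at baseline from a certified rater.
- Section 4.5.1.2 collects date of birth.
- Section 3.1 forbids starting the IV drug beyond 3 hours from last known well, so that time must be known. The same section stratifies randomization by site only.
- Section 4.1.2 excludes "Disability prior to the presenting stroke", defined as a historical mRS of 2 or more. Appendix 1 schedules the mRS only at Days 30 and 90.
- Section 6.4 uses the same three cuts for subgroups, and plans multivariable logistic regression only to explore interactions.

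**The concern.** Cutting a graded prognostic variable in two discards whatever it says about outcome within each band. Under the primary test, a patient with NIHSS 3 counts the same as one with NIHSS 5, and a patient aged 66 the same as one aged 90. Since randomization does not use these factors, the analysis is free to use the values as measured. At stake is some precision in a trial planned at 80% power, obtainable from the same patients and from data the protocol already needs.

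**Working it through.** **Step 1. Reproduce the plan's figure.** Inputs from section 6.1: 0.65 vs 0.74, one-sided 0.025, 80% power; 1:1 allocation from section 3.1. With unpooled variance:

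N = 2 × (1.960 + 0.842)² × (0.65×0.35 + 0.74×0.26) / 0.09² = 2 × 7.849 × 0.4199 / 0.0081 ≈ 814.

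One non-binding futility look at 50% with O'Brien-Fleming-type beta spending multiplies this by 1.0525, giving 856.5 against the stated 856. Then 856 / 0.95² = 948.5 against the stated 948. Both figures reproduce with no covariate adjustment.

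**Step 2. Large-sample calculation.** The variance of the risk difference is V/N, with

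V = 2E[(Y₀−m₀)²] + 2E[(Y₁−m₁)²] + Var(m₁−m₀),

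where Y₀ and Y₁ are the outcomes under control and alteplase, and m₀ and m₁ are their predictions from the chosen covariates. Unadjusted, V = 2×0.65×0.35 + 2×0.74×0.26 = 0.8398. Ignoring the futility loss,

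power = Φ(0.09/√(V/856) − 1.96) = Φ(2.873 − 1.96) = 81.9%.

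The protocol gives no prognostic strengths, so the following are assumptions: NIHSS 0 to 5 in proportions 0.10, 0.22, 0.22, 0.20, 0.15, 0.11; age with mean 62 and SD 13; time triangular on 0.7 to 3.0 hours with mode 2.6; historical mRS of 1 in 25%. Odds ratios are for an unfavorable outcome.

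| OR per NIHSS point / decade / hour / mRS 1 vs 0 | 8 strata: variance cut, power | 8 strata split by mRS: power | Full scale plus mRS: variance cut, power |
|---|---|---|---|
| 1.2 / 1.2 / 1.0 / 1.0 | 1.8%, 82.6% | 82.6% | 2.6%, 82.9% |
| 1.1 / 1.1 / 1.0 / 1.5 | 0.5%, 82.1% | 82.4% | 1.4%, 82.5% |
| 1.2 / 1.2 / 1.1 / 2 | 1.8%, 82.6% | 83.4% | 4.6%, 83.7% |
| 1.3 / 1.3 / 1.2 / 2.5 | 3.5%, 83.3% | 84.5% | 8.4%, 85.1% |
| 1.5 / 1.5 / 1.2 / 3 | 7.4%, 84.7% | 86.3% | 14.8%, 87.6% |

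In the first row time and historical mRS carry no information, so its gain of 82.9 − 82.6 = 0.3 points comes from ungrouping NIHSS and age. In the other four rows the ungrouping step (last column minus the one before) gains 0.1, 0.3, 0.6 and 1.3 points. The whole step from the protocol's strata to full scale plus mRS gains 0.4, 1.1, 1.8 and 2.9 points. In sample-size terms the last row is 856 × (1 − 0.148)/(1 − 0.074) ≈ 787, about 8% fewer patients for equal precision. The second row gives 848, about 1% fewer.

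**Step 3. Simulation, logistic score test.** N=856, 65% vs 74%, 3,000 to 4,000 trials per scenario; assumed log-odds of −0.1 to −0.35 per NIHSS point and −0.01 to −0.04 per year. Ungrouping NIHSS and age gained 0.1 to 1.4 power points over the eight-stratum CMH test. Adding historical mRS (1 in 15–25% of patients, odds ratio 1.5 to 4) brought the total to 1 to 4 points. One-sided error was 2.7% against 2.6% for CMH over 6,000 runs. The Monte Carlo standard error is √(0.025×0.975/6000) = 0.2 points, so the two are indistinguishable.

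**Step 4. Simulation, standardized risk difference (the estimator proposed below).** Also at N=856 with assumed effects. Full-scale NIHSS, age and time gained 0.5 to 1.6 points; with historical mRS, 0.6 to 3.2. No power was lost even when the true effects were steps exactly at the protocol's cut points. One-sided error was 2.7–2.8% against 2.7% for CMH.

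**Combined range.** NIHSS, age and time alone: 0.1 to 1.6 points. With historical mRS: 0.4 to 4 points.

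**The case against.** The strongest reply is that nothing here is an error. A prespecified stratified CMH test controls its type I error, 856 and 948 reproduce without any covariate credit, and the cuts match the subgroup definitions in section 6.4. All of that stands, and it limits the point to a suggestion about efficiency.

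The size is also assumed. The protocol gives no prognostic strengths, and the low end of the range is practically nil. That stands too.

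Four stronger readings are tempting, and the protocol does not support them.
- A reader might infer that every site already scores pre-stroke mRS as 0 or 1 and the analysis ignores it. Section 4.1.2 requires only a judgement that historical mRS is below 2. Neither the Visit 1 list in section 4.6.1 nor Appendix 1 shows 0 vs 1 being recorded.
- A reader might infer that chance imbalance within the bands biases the result. In a randomized comparison it does not; the error rate allows for it, and the strata already deal with imbalance between bands.
- A reader might count the missing risk-difference estimate as a defect, because the hypothesis is stated as a 9-point absolute difference. The estimate that accompanies a CMH test is commonly left to the SAP, which is not at hand, and a Mantel-Haenszel risk difference would fit the text.
- A reader might think the change is free. It is cheap, but the cost is not zero.

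One objection does not stand: that a regression could do worse if the true effects are not linear. In step 4, step-shaped effects at the protocol's own cut points cost no power.

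**Conclusion.** The primary analysis is valid and the sample size needs no change. Section 6.2 gives up a small amount of precision by using three graded baseline variables at two levels each, with nothing in the randomization to require it. The loss is roughly 0.1 to 1.6 power points at N=856 from NIHSS, age and time alone. It rests on assumed odds ratios and covariate distributions, and would be near zero if these variables predict outcome weakly. The larger range, 0.4 to 4 points, depends on historical mRS, which would first have to be recorded. This is an optional improvement, not a correction the trial needs.

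**What to change.** In section 6.2, before unblinding, make the primary analysis a logistic regression of mRS 0–1 on treatment with NIHSS (0–5), age (years) and time from last known well (minutes), reported as the standardized risk difference with 95% CI. Keep the stated CMH test as a sensitivity analysis beside the chi-square test. Say whether the futility look in section 6.5 uses the same model, and give a rule for a missing baseline covariate. An estimate with a standard error also combines directly across the multiple imputations planned in section 6.6.

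Optionally, add one eCRF field for historical mRS (0 vs 1), completed at screening, and include it as a covariate.

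The cost is a change of wording in section 6.2 and routine code; a model-based primary estimate also takes slightly more explaining than a CMH test. The optional covariate adds one data field, best captured prospectively. No extra patients or visits are needed.
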